### Estimating the time taken for a treatment to reach a pre-defined change from baseline value

For a specific treatment group, let  $\{C_{ik}, \log \theta_{ik}\}$  denote the set of estimated model parameters for the  $i$ -th subject from the  $k$ -th posterior sample, where  $i = 1, \dots, n$  and  $k = 1, \dots, 3000$  (assuming the 3 chains are stationary and mix well). Let  $\Delta$  denote a pre-defined change from baseline value, where  $\Delta = 50, 100, 150, 200, 250, \text{ and } 300$  mL. Let  $T$  be the *planned* duration of the study in days, where  $T=84$  is divided into 1000 time points to give  $\{t_1, \dots, t_{1000}\}$ . The time taken to reach a pre-defined change from baseline value will be estimated for benralizumab and placebo by following the steps below:

- i. For the  $k$ -th posterior sample ( $k = 1, \dots, 3000$ ), the fitted change from baseline at time point  $t_j$  ( $j = 1, \dots, 1000$ ) for the  $i$ -th subject ( $i = 1, \dots, n$ ) in a specific treatment group is

$$y_{ik}(t) = C_{ik}(1 - e^{-\theta_{ik}^* t})$$

where  $\theta_{ik}^* = e^{\log \theta_{ik}}$ .

- ii. The mean change from baseline value at time  $t_j$  for the  $k$ -th posterior sample will be calculated as

$$\bar{y}_k(t_j) = \frac{1}{n} \sum_{i=1}^n y_{ik}(t_j)$$

- iii. For pre-BD FEV1, an improvement is associated with  $\Delta > 0$ . Thus, from the set of values  $\{\bar{y}_k(t_1), \dots, \bar{y}_k(t_{1000})\}$ , all values greater than or equal to a specific value of  $\Delta$  will be retained. The earliest time point will be selected and labelled  $t_k^*$  (which gives the earliest time point at which  $\bar{y}_k(t_j)$  is closest to  $\Delta$ ). If there are no values that are greater than or equal to  $\Delta$ , the time  $t_k^*$  will be set to a large value greater than  $T$  (e.g.  $t_k^* = 10000$ ). Consequently, all posterior samples will be included in the summary of  $\{t_1^*, \dots, t_{3000}^*\}$ .
- iv. The 50th and (2.5th, 97.5th) percentiles of  $\{t_1^*, \dots, t_{3000}^*\}$  will be derived, giving the median and corresponding 95% credible interval for the average time taken for the change from baseline to reach  $\Delta$ . If either the 50th, 2.5th or 97.5th percentile is greater than  $T=84$ , such values will be reported as “>84”.
- v. Steps (i) through to (iv) will be carried out for each treatment and all values of  $\Delta$

Note that it is anticipated that some subjects may withdraw from the study early. For these subjects, their fitted response will be extrapolated beyond their last visit. Consequently, inferences will be based on all subjects in the analysis set.

Estimates and credible intervals for the time taken for a treatment to reach a pre-defined change from baseline value from the modelling above will be tabulated by treatment and pre-defined change from baseline value.

### Estimating the time taken for the difference between benralizumab and placebo [change from baseline values] to reach a pre-defined value

Assuming the 3 chains are stationary and mix well, by independence the  $k$ -th posterior sample for benralizumab will be associated with the  $k$ -th posterior sample for placebo ( $k = 1, \dots, 3000$ ). For the  $k$ -th posterior sample, let  $\{C_{ik}, \log \theta_{ik}\}$  denote the set of estimated model parameters for the  $i$ -th subject in the benralizumab group ( $i = 1, \dots, n$ ) and let  $\{D_{il}, \log \beta_{il}\}$  denote the set of estimated model parameters for the  $l$ -th subject in the placebo group ( $l = 1, \dots, m$ ). Let  $\tau$  denote a pre-defined difference between benralizumab and

placebo change from baseline values, where  $\tau = 50, 100, 150, 200, 250,$  and  $300$  mL. Let  $T$  be the *planned* duration of the study in days, where  $T=84$  is divided into 1000 time points to give  $\{t_1, \dots, t_{1000}\}$ . The time taken for the difference between benralizumab and placebo to reach a pre-define value will be calculated as follows:

- i. For the  $k$ -th posterior sample ( $k = 1, \dots, 3000$ ), the fitted change from baseline at time point  $t_j$  ( $j = 1, \dots, 1000$ ) for the  $l$ -th subject ( $l = 1, \dots, m$ ) in the placebo group is

$$u_{lk}(t_j) = D_{lk}(1 - e^{-\beta_{lk}^* t_j})$$

where  $\beta_{lk}^* = e^{\log \beta_{lk}}$  and the mean change from baseline value at time  $t_j$  for the  $k$ -th posterior sample will be calculated as

$$\bar{u}_k(t_j) = \frac{1}{m} \sum_{l=1}^m u_{lk}(t_j)$$

- ii. For the  $k$ -th posterior sample ( $k = 1, \dots, 3000$ ), the fitted change from baseline at time point  $t_j$  ( $j = 1, \dots, 1000$ ) for the  $i$ -th subject ( $i = 1, \dots, n$ ) in the benralizumab group is

$$v_{ik}(t_j) = C_{ik}(1 - e^{-\theta_{ik}^* t_j})$$

where  $\theta_{ik}^* = e^{\log \theta_{ik}}$  and the mean change from baseline value at time  $t_j$  for the  $k$ -th posterior sample will be calculated as

$$\bar{v}_k(t_j) = \frac{1}{n} \sum_{i=1}^n v_{ik}(t_j)$$

- iii. For the  $k$ -th posterior sample ( $k = 1, \dots, 3000$ ), the average difference between benralizumab and placebo at time point  $t_j$  will be calculated as

$$\bar{d}_k(t_j) = \bar{v}_k(t_j) - \bar{u}_k(t_j)$$

- iv. For pre-BD FEV1, an improvement is associated with  $\tau > 0$ . Thus, from the set of values  $\{\bar{d}_k(t_1), \dots, \bar{d}_k(t_{1000})\}$ , all values greater than or equal to a specific value of  $\tau$  will be retained. The earliest time point will be selected and labelled  $t_k^*$  (which gives the earliest time point at which  $\bar{d}_k(t_j)$  is closest to  $\tau$ ). If there are no values that are greater than or equal to  $\tau$ , the time  $t_k^*$  will be set to a large value greater than  $T$  (e.g.  $t_k^* = 10000$ ). Consequently, all posterior samples will be included in the summary of  $\{t_1^*, \dots, t_{3000}^*\}$ .

*Note that for a secondary variable an improvement could be associated with  $\tau < 0$ .*

*Thus, from the set of values  $\{\bar{d}_k(t_1), \dots, \bar{d}_k(t_{1000})\}$ , all values less than or equal to a specific value of  $\tau$  will be retained. The earliest time point will be selected and labelled  $t_k^*$  (which gives the earliest time point at which  $\bar{d}_k(t_j)$  is closest to  $\tau$ ). If there*

are no values that are less than or equal to  $\tau$ , the time  $t_k^*$  will be set to a large value greater than  $T$  (e.g.  $t_k^* = 10000$ ). Consequently, all posterior samples will be included in the summary of  $\{t_1^*, \dots, t_{3000}^*\}$ .

- v. The 50th and (2.5th, 97.5th) percentiles of  $\{t_1^*, \dots, t_{3000}^*\}$  will be derived, giving the median and corresponding 95% credible interval for the average time taken for the average difference between benralizumab and placebo to reach  $\tau$ . If either the 50th, 2.5th or 97.5th percentile is greater than  $T=84$ , such values will be reported as “>84”.
- vi. Steps (i) through to (v) will be carried out for all values of  $\tau$

Estimates and credible intervals for the time taken for the difference between benralizumab and placebo [change from baseline values] from the modelling above will be tabulated by treatment and pre-defined difference value.

### Estimating the proportion of subjects $\geq$ pre-defined thresholds at time points of interest

For a specific treatment group, let  $\{C_{ik}, \log \theta_{ik}\}$  denote the set of estimated model parameters for the  $i$ -th subject from the  $k$ -th posterior sample, where  $i = 1, \dots, n$  and  $k = 1, \dots, 3000$  (assuming the 3 chains are stationary and mix well). Let  $t$  denote a time point of interest, where  $t=1, 3, 7, 14, 21, 28, 58, 84$ . Let  $\Delta$  denote a pre-defined change from baseline value, where  $\Delta= 50, 100, 150, 200, 250, \text{ and } 300$  mL. At a specific time point, the proportion of subjects  $\geq \Delta$  will be estimated for benralizumab and placebo by following the steps below:

- i. For the  $k$ -th posterior sample ( $k = 1, \dots, 3000$ ), the fitted change from baseline at time point  $t$  for the  $i$ -th subject ( $i = 1, \dots, n$ ) in a specific treatment group is

$$y_{ik}(t) = C_{ik}(1 - e^{-\theta_{ik}^* t})$$

where  $\theta_{ik}^* = e^{\log \theta_{ik}}$ .

- If, at time point  $t$ :  
 $y_{ik}(t) \geq \Delta$  set  $I_{ik} = 1$   
 otherwise set  $I_{ik} = 0$

- The proportion of subjects will be calculated as

$$p_k = \frac{1}{n} \sum_{i=1}^n I_{ik}$$

- iv. The 50th and (2.5th, 97.5th) percentiles of  $\{p_1, \dots, p_{3000}\}$  will be derived, giving the median and corresponding 95% credible interval for the proportion of subjects greater than or equal to a specific value of  $\Delta$  at time point  $t$ .
- v. Steps (i) through to (iv) will be carried out for each treatment and all values of  $t$  and  $\Delta$

Estimates and credible intervals for the proportion of responders  $\geq$  pre-defined thresholds at time points of interest from the modelling above will be tabulated by treatment, pre-defined thresholds and timepoints of interest.

### Estimating the difference between proportions

Following the steps outlined in Section 5.4, let  $\{p_1, \dots, p_{3000}\}$  denote the set of proportions for benralizumab and let  $\{q_1, \dots, q_{3000}\}$  denote the set of proportions for placebo for a specific value of  $t$  and  $\Delta$ .

- i. For the  $k$ -th posterior sample ( $k = 1, \dots, 3000$ ), calculate the difference
$$d_k = p_k - q_k$$
- ii. The 50th and (2.5th, 97.5th) percentiles of  $\{d_1, \dots, d_{3000}\}$  will be derived, giving the median and corresponding 95% credible interval for the difference between proportions
- iii. Steps (i) through to (ii) will be carried out for all values of  $t$  and  $\Delta$

Difference of proportions between treatment groups over time will be tabulated for each pre-defined threshold. Figures will be provided.

### Estimating the odds ratio

Following the steps outlined in Section 5.4, let  $\{p_1, \dots, p_{3000}\}$  denote the set of proportions for benralizumab and let  $\{q_1, \dots, q_{3000}\}$  denote the set of proportions for placebo for a specific value of  $t$  and  $\Delta$ .

- i. For the  $k$ -th posterior sample ( $k = 1, \dots, 3000$ ), calculate the odds ratio
$$o_k = \frac{p_k / (1 - p_k)}{q_k / (1 - q_k)}$$
- ii. The 50th and (2.5th, 97.5th) percentiles of  $\{o_1, \dots, o_{3000}\}$  will be derived, giving the median and corresponding 95% credible interval for the odds ratio
- iii. Steps (i) through to (ii) will be carried out for all values of  $t$  and  $\Delta$

In the cases when proportions of responders or non-responders in either treatment group is zero, odds ratio would be estimated using the following approach:

- i) calculation of odds ratio on iteration level: when proportion of responders or non-responders is 0 in a treatment group, make adjustment by adding 0.5 to all cell counts, eg out of N=100 in a treatment arm, if there is 0 responder, and 100 non-responders observed in an iteration, replace the count of responder with 0.5, and non-responder with 100.5 in that treatment arm. And add 0.5 to cell counts in the other treatment arm. Then calculate odds ratio for that

iteration. This applies to cases when 0 count occurs in either or both Benra and Placebo groups.

ii) summary statistics across 3000 iterations: if more than 5% odds ratios are estimated as outlined in step i) due to 0 count, then set the estimates (median, 95% credible intervals) to NC; otherwise, median, and 95% credible intervals are based on 3000 iteration results with estimated odds ratios (as outlined in step i) included.

Odds ratio over time will be tabulated for each pre-defined threshold. Figures will be provided.

### **Alternative models**

Convergence issues may arise when carrying out the planned analysis and it may be deemed necessary to consider alternatives for (i) the set of priors, (ii) the distributions associated with the model parameters describing the data and (iii) the exponential model.

However, if such changes still lead to convergence issues, a simplified analysis will be carried out whereby an exponential model (or alternative) will be fitted through the mean change from baseline values for each treatment. Consequently, focus will be based on point estimates only, without any measures of precision, given that between-subject and within-subject components could not be incorporated in the model successfully. In this case, we will estimate

- i. the change from baseline at  $t=3,7,14,28,56,84$
- ii. the time taken for benralizumab and placebo to reach  $\Delta = 50, 100, 150, 200, 250,$  and  $300$  mL
- iii. the time taken for the difference between benralizumab and placebo change from baseline values to reach  $\tau = 50, 100, 150, 200, 250,$  and  $300$  mL

Note that all deviations from the planned analysis will be documented as a change in the statistical analysis plan

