## 1.3 Number of subjects

The study will recruit approximately 230 patients in total and 115 patients in each treatment group based on the primary objective of the study to determine the effect of benralizumab on the time course of change (onset and maintenance of effect) of pre-bronchodilator (BD) FEV1.

Patients will be randomized in a 1:1 ratio to benralizumab or placebo. In order to have a balanced number of patients for each region and the body plethysmography sub-study, the randomization will be stratified by these variables.

The study is powered for the primary objective of the study to determine the effect of benralizumab on the time course of change (onset and maintenance of effect) of pre-BD FEV1.

The first post-baseline timepoint where the p-value for the mean difference between benralizumab and placebo is  $\leq 0.05$  will be used to determine time to onset of effect. The average over the mean differences between benralizumab and placebo based on the change from baseline (Visit 4) to Days 28 (Visit 8), 56 (Visit 9), and 84 (Visit 10) in pre-BD FEV1 will be used to determine if the study is positive and to determine maintenance of effect.

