The results of the Phase 2b study, MI-CP220 (Castro et al 2014) and the Phase 3 asthma exacerbation studies, SIROCCO (Bleeker et al 2016) and CALIMA (Fitzgerald et al 2016) were used as a basis for the sample sizing. From these studies, it is expected that around 115 patients per treatment arm (230 in total) will provide approximately 90% power for the primary endpoint pre-BD FEV1 with type I error controlled at a two-sided alpha level of 0.05 if the true average over the mean treatment differences (benralizumab – placebo) across Days 28 (Visit 8), 56 (Visit 9), and 84 (Visit 10) is 138 mL. The sample size will also be sufficient to have approximately 80% power for an average over the mean treatment difference of 120 mL. The assumed variability has a within-group standard deviation of 375 mL and within-patient correlation of 0.6. If the within-patient variability is reduced to 350 mL, the sample size would be sufficient 80% power for an average of 110 mL. In addition, it is expected that around 115 patients per treatment arm will have 80% power to detect a true treatment difference (benralizumab – placebo) of 130 mL, assuming a within-group standard deviation of 350 mL or a true treatment difference of 140 mL, assuming a standard deviation of 375 mL. Based on these assumptions, the minimum difference that would be statistically significant at the 5% level ranges from approximately 85 to 100 mL. The sample size was estimated using nQuery + nTerim version 3.0 using methodology by Liu et al (Liu et al 2005).

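### Minor: if the onset model will not converge, the SAP's fallback reports onset times with no interval, for a reason that does not follow; resampling patients would supply one cheaply

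*SAP*

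**What the plan says.** SAP 4.2.5.4 fits an exponential nonlinear mixed-effects model to pre-BD FEV1 change from baseline, by Bayesian methods, separately in each arm. It gives a median and 95% credible interval for the change at chosen days, the time for each arm to reach 50 to 300 mL, and the time for the between-arm difference to reach 50 to 300 mL. Thresholds not reached within 84 days are reported as >84.

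The Alternative models paragraph covers failure. If convergence problems persist after trying other priors, distributions and curves, the rule, applied arm by arm, is that "a simplified analysis will be carried out whereby an exponential model (or alternative) will be fitted through the mean change from baseline values". Then "focus will be based on point estimates only, without any measures of precision", because between- and within-subject components could not be built into the model. The three kinds of quantity above are still to be estimated. The SAP contains no bootstrap and no other interval method for this branch. It does say that deviations from the planned analysis will be documented.

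**The concern.** The fallback curve is fitted to arm means and contains no random effects. Failure to fit random effects is therefore no reason to leave out the uncertainty of that curve. Its sampling error comes from which patients happen to be in each arm, and the data show this directly. Resampling whole patients, with all their visits, carries between-patient and within-patient variation into the means together.

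At stake is how an onset time would be read. In the planned analysis a time to 50 or 100 mL comes with an interval. In the fallback the same quantity would appear as a bare number of days, although at this sample size it is poorly determined. The primary analysis gives intervals for differences at visits, but none for a time to threshold.

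**Working it through.** **1. Inputs from the documents.** SAP 1.3: 115 per arm, 1:1, two-sided 0.05, "within-group standard deviation of 375 mL and within-patient correlation of 0.6". SAP 4.2.5.4: visits at Days 3, 7, 14, 28, 56 and 84, a time grid of 84 days cut into 1000 points, and the >84 rule.

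**2. The plan's own figure.** The fallback paragraph states no figure, so the check on inputs is the power statement.
- SD of a three-visit average: 375 × √((1 + 2 × 0.6)/3) = 321.1 mL.
- SE of the difference: 321.1 × √(2/115) = 42.35 mL.
- For 138 mL: 138/42.35 − 1.960 = 1.299, which gives 90.3% power. The plan says it "will provide approximately 90% power for the primary endpoint".
- The 120 mL case gives 80.9%. The 110 mL case with SD 350 mL gives 79.5%. Both match the stated 80%.

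**3. Assumptions.** The documents give no curves. The main case takes the true difference as

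d(t) = 220(1 − 2^(−t/7)) − 80(1 − 2^(−t/3)).

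At Days 28, 56 and 84 this is 126.4, 139.1 and 139.9 mL, averaging 135 mL against the design's 138 mL. It reaches 50 mL at 7.6 days and 100 mL at 16.8 days (16.9 on the SAP's grid). The correlation of 0.6 is stated for the power calculation and is extended here to all visits.

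**4. Why the crossing time is poorly determined.** The SE of a difference at one visit is 375 × √(2/115) = 49.5 mL, so a 95% half-width is 1.96 × 49.5 = 97 mL. The true differences at Days 7 and 14 are 46 and 88 mL. Fitting a curve pools visits and helps, but not enough.

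**5. Spread of the point estimate.** Trials were simulated with the inputs above, complete data and least-squares curves through the arm means. True times come from setting d(t) = 50.

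| Plateaus, benralizumab/placebo (mL) | Half-times (days) | True time to 50 mL (days) | Central 95% of estimates (days) |
|---|---|---|---|
| 220/80 | 7/3 | 7.6 | about 2 to 38 |
| 220/80 | 3/3 | 1.9 | 0.8 to 14 |
| 220/80 | 14/3 | 17.8 | 4 to 69 |
| 250/50 | 7/7 | 2.9 | 1.2 to 12 |

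Upper ends move by a few days between simulation runs. In the first case the time to 100 mL runs from 4.5 days to >84, and about 16% of trials never reach it. In the last case, where the plateau difference is 200 mL, 0.6% never do.

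**6. Whether a bootstrap supplies the missing interval.** Whole patients were resampled within arm and the curve was refitted each time.
- *Complete data, correct curve.* In the main case, coverage of the times to 50 and 100 mL was 94% to 96%. With other assumed curves (asymptotes 300 vs 160 mL and 260 vs 122 mL) it was 94% to 97% for thresholds reached before Day 84. In the 300 vs 160 mL case with both rates 0.1/day, the true time to a 100 mL difference is 12.6 days. The median estimate was 12.4 days, the median interval was 3.8 to >84 days, and the upper limit passed Day 84 in 80% of trials.
- *Outcome-dependent dropout, raw means.* With an assumed 14% missing at Day 84, coverage of the benralizumab change fell to 83% at Day 56 and 79% at Day 84, and for its time to 300 mL to 78%. Differences kept 94% to 95%, with the same dropout rule in both arms. With 19% missing, coverage of the Day 84 benralizumab change was 52%.
- *Outcome-dependent dropout, MAR means.* In the 19% case, refitting likelihood-based visit means in each resample restored 95% coverage at Days 56 and 84, and for the difference reaching 50 mL.

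**The case against.** The strongest case against acting is that this branch may never be used. It is reached only after priors, distributions and the curve have all been varied, and it belongs to a supportive analysis. Study success and the primary onset rule rest on the MMRM in SAP 4.2.5.1, which reports 95% confidence intervals and p-values at each visit. FEV1 responders at the same six thresholds are also modelled by visit (SAP 3.2.1 and 4.2.6.1). The SAP is open that the fallback has no precision. All of this stands, and it keeps the point minor. None of it gives an interval for a time to threshold.

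A reader might infer that the SAP declares precision impossible. It does not: it says precision will be omitted and gives a reason, and only the reason fails.

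A reader might also infer that a bootstrap gives valid intervals at no cost. That is too strong. SAP 4.2.5.4 expects some early withdrawal. Raw means lack the missing-at-random protection that Appendix 8.1 claims for the MMRM, and two of the three fallback quantities include within-arm results, where under-coverage appeared. Nor does resampling repair a badly chosen curve, and this branch is entered when fitting has already gone wrong.

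**Conclusion.** The point holds as a cheap improvement of minor severity. The fallback omits precision for a reason that does not follow, and departs from the SAP's own practice of giving intervals for the same quantities.

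The omitted uncertainty is large. In the main assumed case, a true 7.6 days to a 50 mL difference is estimated anywhere from about 2 to 38 days. Other curves gave ranges from about 1 to 12 days up to 4 to 69 days. No single range should be read as a property of this trial: each depends on assumed plateaus and half-times, and on extending the 0.6 correlation to the early visits. What carries across the cases is that the ranges are wide.

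It would be wrong to infer that the trial's onset conclusion is in doubt. The primary MMRM and the conclusion drawn from it are unaffected.

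**What to change.** Replace the no-precision sentence in Alternative models with a rule such as this: 95% percentile intervals for the fallback quantities will come from a bootstrap of whole patients, stratified by arm; in each resample the visit means will be re-estimated with an MMRM of the primary-analysis form and each arm's curve refitted to them; limits not reached by Day 84 will be reported as >84. Also state the number of resamples, the seed, and what is done if the MMRM fails to converge in a resample. Point estimates should use the same model-based means.

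The cost is a short SAP edit, a little code and more computing time. There are three downsides to accept. The curve is fitted to model-based rather than raw means, which changes the fallback's input. The intervals are only approximate, and only if the chosen curve fits and data are missing at random. Many intervals will be open-ended, which fairly reflects how little the data say about a crossing time.
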